## 6.0 Inclusion and Exclusion Criteria

6.1 *Describe the criteria that define who will be **included** in your final study sample.*

*NOTE: This may be done in bullet point fashion.*

*Response: **Inclusion Criteria***

- Type 1 Diabetes for at least 1 year on stable use of continuous subcutaneous insulin infusion (CSII) or multiple (four or more) injections of insulin per day for last 3 months.
- HbA1c of 7-10% (inclusive)
- Ages 18-65 years (inclusive of ages 18 and 65)
- BMI  $\geq$  22 kg/m^2.
- Well versed in CHO counting.

6.2 *Describe the criteria that define who will be **excluded** from your final study sample.*

*NOTE: This may be done in bullet point fashion.*

*Response: **Exclusion Criteria***

- Inability to give informed consent
- Inability or refusal to comply with protocol
- Use of GLP-1 Receptor Agonists in the last 3 months or DPP-IV and SGLT-2 inhibitors therapy in the last 1 month.
- Risk for pancreatitis (e.g., history of gallstones, alcohol abuse, and hypertriglyceridemia)
- History of pancreatitis and or chronic pancreatitis
- Coronary event or procedure (myocardial infarction, unstable angina, coronary artery bypass, surgery or coronary angioplasty) or stroke in the previous 3 months.
- Congestive Heart Failure class III or IV or tachyarrhythmia.

- Hepatic disease: Severe hepatic insufficiency and/or significant abnormal liver function defined as:
  1. Aspartate aminotransferase (AST) >3x upper limit of normal (ULN) and/or alanine aminotransferase (ALT) >3x ULN
  2. Total bilirubin >2.0 mg/dL (34.2 µmol/L)
  3. Positive serologic evidence of current infectious liver disease including Hepatitis B viral antibody IGM, Hepatitis B surface antigen and Hepatitis C virus antibody
  4. Liver function tests more than 3 times the upper limit of normal
- Renal impairment (e.g., serum creatinine levels  $\geq$ 1.4 mg/dL for women, or eGFR <60 mL/min/1.73 m^2) or history of unstable or rapidly progressing renal disease or end stage renal disease.
- History of unexplained microscopic or gross hematuria, or microscopic hematuria at visit 1, confirmed by a follow-up sample at next scheduled visit.
- HIV positive
- History of gastroparesis
- History of medullary thyroid carcinoma or MEN 2 syndrome
- History of recurring UTI
- Uncontrolled thyroid disease (documented normal TSH), Cushing's syndrome, congenital adrenal hyperplasia or hyperprolactinemia.

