In the acute effects study, qualified patients will come fasting to the research center. Review of study procedures and vitals will be performed. Insulin infusion (pump) will be stopped and basal blood, urine and adipose tissue biopsy samples will be obtained. Placebos, exenatide (5µg) or dapagliflozin (10mg) (with appropriate placebos) or combination of exenatide and dapagliflozin will be administered, according to a randomized fashion and cohort assigned, and blood samples will be collected every 30 min for up to 8 hours after starting the treatment. Urine will be collected every hour up to 8 hours and a second adipose tissue biopsy will be collected at 6 hours after the start of the treatment. Additional blood samples will be collected at 1, 2, 4 and 6 and 8 hour marks for MNC isolation. Plasma and mononuclear cell (MNC) fractions will be prepared from the blood samples. The patient will then come back at the 24 hour mark for a fasting blood and urine collection. The long term study will then commence. Depending on the cohort, Exenatide extended release or dapagliflozin (along with appropriate placebos) or a combination of both drugs will be started and continued for 12 weeks according to original randomization of day 0. In the long term study, dapagliflozin (or the appropriate placebo) will be started at 5mg dose and will be titrated to 10mg/day after 5 days. Fasting blood and 24hr urine samples will be collected at 1, 4 and 8 weeks. At 12 weeks, the 2nd acute effects testing study will be repeated as described above.

Drug Blinding:

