**Visit 6 (Week 12):** Subjects will be asked to come for the visit in a fasting state (10-12hr fasting). The will be fasting for the entire visit. Once the patient arrives to the research center, a complete physical examination will be done, 24hr urine will be collected, vitals and fingerstick blood glucose and ketones ( $\beta$ -hydroxybutyrate) using the Precision Extra glucose and ketones meter (Abbott Laboratories) will be measured. For MDI patients, baseline blood, spot urine, and adipose tissue will be collected. The remainder of this visits' procedures apply only to pump patients. An IV port will be placed in order to obtain blood samples throughout the duration of the visit. Insulin infusion will be stopped. Baseline blood, spot urine, and adipose tissue will be collected immediately after stopping insulin. One of the treatment arms will be administered to the patient according to their original group assignment as in Visit 2. All samples and monitoring procedures will be done as in Visit 2. Insulin doses will be titrated to target blood glucose between 70-180 mg/dl if

possible at all times without having additional hypoglycemia (less than 70 mg/dl) before discharge from study.

Phone calls will be made by our team at weeks 2, 6 and 10 to ensure safety. Patients will also be instructed to call if they develop unexpected symptoms.

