#### *Response:*

Measurements of beta-hydroxybutyrate, acetoacetic acid, glucose, FFA and glucagon, will be measured from all blood samples collected. HSL, GLP-1, glycerol, electrolytes, serum bicarbonate, cortisol and catecholamines will be measured at 0, 60, 120, 240, 360, 480 min and at 24hr following single dose studies at 0 and 12 weeks visits and at baseline on the 1, 4 and 8 weeks visits. Ketone bodies will be measured in all urine samples. All MNC and adipose tissue samples will be tested for HSL and SGLT2 expression, as in the table below.

Visit #	Screening	1	2	3	4	5	6
Day #		-7	0	8 week 1	28 week 4	56 week 8	84 week 12
Study Procedures	Screening	Insulin titration	Single dose test	2 days after up titration			End long term/ Single dose test
History	X						
Physical	X				X		X
CBC	X						X
CMP/lipid profile	X				X		X
Vitals and BP	X	X	X	X	X	X	X
Pregnancy test	X				X	X	X
HbA1c	X						X
Plasma ketone bodies and metabolic end points			X	X	X	X	X
Urine ketone bodies and oxidative stress end points			X	X	X	X	X
Insulin injection log/Glucose/CGM/pump and food diary review/Insulin dose titrations		X Review of glucose/Insulin doses	X	X	X	X	X
Adipose tissue biopsy			X				X

 10.3 List any instruments or measurement tools used to collect data (e.g. questionnaire, interview guide, validated instrument, data collection form).

*Include copies of these documents with your submission.*

Response: Source documents will be used to collect patient information. The CGM or insulin pump will be used to collect glucose and insulin data, Glucose and ketone meter will be used to measure glucose and ketone in blood. Ketostix for measuring ketones in urine. Food diary will be used to collect food intake.

10.4 Describe any source records that will be used to collect data about subjects (e.g. school records, electronic medical records).

Response: electronic medical records and research files.

10.5 Indicate whether or not **individual** subject results, such as results of investigational diagnostic tests, genetic tests, or incidental findings will be shared with subjects or others (e.g., the subject's primary care physician) and if so, describe how these will be shared.

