## 17.0 Data Management and Analysis

17.1 *Describe the data analysis plan, including any statistical procedures. This section applies to both quantitative and qualitative analysis.*

Response: **DATA ANALYSIS**

This is a prospective study to evaluate ketogenic stress before and after 12 week treatment with dapagliflozin and exenatide/Bydureon. The similarities in baseline values between the study groups will be compared using appropriate parametric tests. Transformations of the data on order to meet statistical assumptions may be considered. All statistical analysis will be carried out using SPSS software (SPSS Inc, Chicago, Illinois) based on intention to treat principle. Data will be presented as mean± standard error. *Data will not be imputed to replace missing data and only observed data will used to run the mixed model for repeated measurement (MMRM) analysis. The primary endpoint of the study is to detect a significant difference in the percent change in beta-hydroxybutyrate and acetoacetic acid (total ketone bodies) in the plasma samples following 12 weeks of dapagliflozin treatment compared to placebo. *Fasting samples collected at weeks 0, 1, 4, 8 and 12 will be used for this comparison with values at week 0 considered as baseline. The statistical analysis will be done using MMRM with assigned  $\alpha$  value of 0.05. There is no previous data on effects of dapagliflozin alone on ketone bodies generation in T1D but our preliminary data on 12 weeks treatment with**

dapagliflozin in patients with T1D using insulin and liraglutide shows more than a 2 fold increase in total ketone bodies.

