The secondary end points include the *comparison of the acute changes in AUC0hr-6hr of ketone bodies (plasma and urine), FFA and glucagon between dapagliflozin, exenatide, combination of both and placebo before and after 12 weeks of treatment period using Paired t-test for within group comparisons and student t-test for between groups comparisons.* Additional secondary end points include comparison of basal plasma glucagon, FFA and urinary ketone bodies changes after 12 weeks of dapagliflozin and Bydureon or combination of both treatments compared to baseline using paired t-test and to placebo using 2-way RMANOVA. Changes in insulin dose, glucose levels and carbohydrate intake will be compared after 12 weeks of dapagliflozin and Bydureon treatments to baseline using paired t-test and to placebo with 2-way RMANOVA. Changes in lipolysis mediator (HSL) in plasma and expression of HSL and SGLT-2 in adipose tissue and MNC will be compared to baseline using paired t-test and to placebo with t-test.

*17.2 If applicable, provide a power analysis.*

*NOTE: This may not apply to certain types of studies, including chart/records reviews, survey studies, or observational studies. This question is asked to elicit whether the investigator has an adequate sample size to achieve the study objectives and justify a conclusion.*

*Response:* Conservatively estimating a difference in the change from baseline in ketone bodies generation between the dapagliflozin and placebo of 50%, with standard deviation of no more than 50%, a sample size of 20 patients per group (assuming a drop-out rate of 15%) should provide adequate power ( $\beta = 0.2$ ) to detect a significant difference ( $\alpha = 0.05$ ). A total of 80 patients will be recruited for the study.

*17.3 Describe any procedures that will be used for quality control of collected data.*

*Response:* Data will not be imputed to replace missing data and only observed data will be used to run the mixed model for repeated measurement (MMRM) analysis

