Safety data (vitals, CBC, CMP, urinary markers) will be collected at screening, during and at end of the study. STAT CMP will be done when glucose or ketones exceeds 400mg/dl and 2.5mM, respectively or any signs of DKA is observed during the acute testing phase. If, ketones measure positive in blood or in urine ( $\geq 0.4$  mM in blood or  $>+1$  in urine) or fasting blood glucose  $<70$  or  $>250$  mg/dl, the acute testing will not take place and patient will be rescheduled. Injection site reactions, mycotic infections and complications of IV and biopsy collection will also be monitored, volume control and hypoglycemia will be monitored and collected at every visit. Physical examination will be performed at 2, 4, 8 and 12 weeks visits and safety assessments performed. Ketone bodies will measured daily by patient in urine. LDL-C levels will be monitored at screening visit, 4 and 12 weeks. Pregnancy will be tested at screening, 4 and 12 weeks. Insulin dose titration will done at every visit to avoid hypoglycemia. Phone calls will be made for safety and compliance follow-up at least 3 time during the study. The patients, however, will be instructed to

report any adverse event or safety related information via phone as soon as it occurs. All safety data will be reviewed by the PI or sub-investigators within 1-2 days of collection.

If the BG concentrations exceed 400 mg/dl or blood  $\beta$ -hydroxybutyrate exceeds 2.5mmol/l (or +3 (80mg/dl) or greater in urine) anytime during the 360 minutes following single dose/doses with no clinical signs and symptoms of DKA like nausea and vomiting then blood sample, spot urine and adipose tissue biopsy will be collected immediately, basal insulin will be restarted; bolus insulin as per the bolus wizard calculator will be administered and a meal provided. Patients will be instructed to come back at the 24-hour mark.

Patients will be instructed to measure ketone bodies in urine samples daily with Ketostix (Bayer) and record it in diary provided. If ketone bodies in urine measure +2 or greater (>4mM in urine), patients are required to notify the research center.

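### If the acute-test ketone limit is applied at week 12, a deferred pump patient has no described fasting plasma draw that day, so the draw should be taken on arrival (low severity)

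*Combined protocol and SAP*

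**What the plan says.** **The limit.** Section 10.1, Visit 2, places the limit among the steps that apply to pump patients only, before the IV port, the insulin stop and the baseline blood. A patient over it does not start: "the acute testing will not take place and patient will be rescheduled". Section 21.2 repeats the rule for the acute testing and names no visit.

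**Week 12.** The overview in section 10.1 calls week 12 the second acute test and says the "acute effects testing study will be repeated as described above". The Visit 6 text includes a fingerstick ketone reading on arrival, but neither the limit nor the arrival Ketostix check. It refers samples and monitoring back to Visit 2. For pump patients it says: "Baseline blood, spot urine, and adipose tissue will be collected immediately after stopping insulin".

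**Injection (MDI) patients.** Section 6.1 admits patients on "multiple (four or more) injections of insulin per day for last 3 months". At both acute-test visits they are sampled without the pump-only steps: "For MDI patients, baseline blood, spot urine, and adipose tissue will be collected".

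**Use of the sample.** Section 17.1 compares percent change in total plasma ketones between dapagliflozin and placebo by MMRM on observed data, without imputation: "Fasting samples collected at weeks 0, 1, 4, 8 and 12 will be used for this comparison with values at week 0 considered as baseline". Secondary endpoints include "comparison of basal plasma glucagon, FFA and urinary ketone bodies changes after 12 weeks of dapagliflozin and Bydureon". The schedule in section 10.2 heads Visit 6 "End long term/ Single dose test" and marks plasma ketones as due.

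**The concern.** The limit screens on beta-hydroxybutyrate, which is one of the two components of the primary endpoint. If it is applied at week 12 and no plasma is taken from a deferred patient, the week-12 value is either missing because it was high, or replaced by a value from a later day chosen because the meter read low. Few placebo patients would be affected, whereas dapagliflozin is expected to raise ketones towards the limit. The selection would therefore act mainly in one arm and shrink the difference the trial is designed to detect.

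MMRM on observed data recovers part of a missing high value through weeks 1, 4 and 8, which carry no limit. It recovers nothing when a low-day value has been substituted. Fasting glucagon and FFA come from the same draw, and a patient without a week-12 value drops out of their paired tests. No loss is computed for these two, because the documents give no correlation with ketones.

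**Working it through.** **1. The plan's own figure.** Section 17.2 assumes a 50% difference, SD 50%, alpha 0.05 (taken as two-sided) and power 0.80. The normal formula gives n = 2 × (1.96 + 0.84)² × (50/50)² = 15.7, so 16 per group. The t-test version gives 17, and 17/0.85 = 20, as stated. This point does not dispute that figure. The 50% serves only as a benchmark.

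**2. Ketone inputs.** Section 3.1 reports 10 retrospective patients on insulin and liraglutide, before and after 12 weeks of dapagliflozin. Beta-hydroxybutyrate went from 0.11 ± 0.02 to 0.39 ± 0.09 mM and acetoacetate from 0.32 ± 0.09 to 0.53 ± 0.11 mM. Reading ± as a standard error:
- coefficient of variation, beta-hydroxybutyrate: 0.09 × √10 / 0.39 = 0.730
- coefficient of variation, acetoacetate: 0.11 × √10 / 0.53 = 0.656
- total before: 0.11 + 0.32 = 0.43 mM; after: 0.39 + 0.53 = 0.92 mM; rise 0.92/0.43 − 1 = 114%

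**3. Assumptions not in the documents.** Log-normal ketones, 15% meter error, placebo flat, and half the patients on pumps. Section 21.1 sets an insulin floor and a 5 mg option that may keep ketones lower, so lower treated means are shown too, with acetoacetate scaled in proportion.

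**4. Share at or above 0.4 mM.** At the pre-dapagliflozin mean of 0.11 mM it is under 1%. On dapagliflozin:

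| Treated beta-hydroxybutyrate mean (mM) | 0.39 | 0.30 | 0.25 | 0.20 |
|---|---|---|---|---|
| Pump patients deferred | 36% | 23% | 15% | 9% |
| Total ketones (mM) | 0.920 | 0.762 | 0.675 | 0.588 |
| True rise from 0.43 mM | 114% | 77% | 57% | 37% |

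**5. Loss if the patient returns until the meter reads below 0.4 mM.** Simulated with within-patient correlation 0–0.8 and log-correlation between the two ketones 0–0.9. Loss = pump share × (true total − sampled total) / (true total − 0.43).
- Highest case (mean 0.39, correlations 0 and 0.9): the sampled total is 0.596, so 0.5 × (0.920 − 0.596) / (0.920 − 0.430) = 0.5 × 0.661 = 33%.
- Lowest case (mean 0.20, correlations 0.8 and 0): the sampled total is about 0.569, so 0.5 × (0.588 − 0.569) / (0.588 − 0.430) = 0.5 × 0.120 = 6%.
- Ranges across the four means: about 9–33%, 8–30%, 7–28% and 6–26%. The low end at 0.39 mM moves between about 8% and 11% with the handling of patients who keep failing the limit.
- The loss is proportional to pump share: half as large at 25%, double at 100%.

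**6. Loss if the patient simply has no week-12 value.** Week 12 was predicted by regression on weeks 1, 4 and 8, with equal means at all four visits and within-patient correlation 0.3–0.8. The loss is about 3–23% at every treated mean.

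**7. If the reported effect is averaged over weeks 1, 4, 8 and 12.** Section 17.1 does not say which contrast is meant. One affected visit in four divides the loss by 4: 33/4 ≈ 8% and 6/4 ≈ 1.5% for step 5, and about 1–6% for step 6. Overall this is about 1–8%.

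**8. Against the planned 50%.** Taking the largest loss at each mean, the rise that remains is 114 × 0.67 ≈ 76%, 77 × 0.70 ≈ 54%, 57 × 0.72 ≈ 41% and 37 × 0.74 ≈ 27%. It falls below plan only where the true rise is already near or under 50%.

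Glucose deferrals are not modelled, because the documents give no data for them.

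**The case against.** The strongest reply is that neither step of the argument is prescribed. Visit 6 follows Visit 2 closely yet leaves out the limit and the Ketostix check. The overview that says the test is repeated contains no limit in its own description of the test. The reference back to Visit 2 comes after the dosing step and most naturally covers sampling and monitoring after the dose. That leaves section 21.2, which repeats the Visit 2 sentence in a risk summary. Further, the rule cancels the acute test and not the visit: the schedule and section 17.1 still call for week-12 plasma, and nothing says to withhold it.

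All of this stands as a limit on what can be claimed. A reader might infer that the protocol excludes high-ketone patients from the week-12 primary sample, or that the primary result is lost. The documents support neither. They leave both questions open, and the result of the unfavourable reading is dilution at one visit of four.

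The reply does not remove the point. Section 21.2 is worded for the acute testing in general, and six hours without insulin in a ketone-positive patient on dapagliflozin is the situation it guards against, so a careful site could well apply it at week 12. That site would then find no instruction on when to take plasma from a deferred pump patient.

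It is also fair that the size rests on an assumed pump share, assumed correlations, unlimited rescheduling and ten patients who were also taking liraglutide. Section 17.1 itself says there are no earlier data on dapagliflozin alone. At within-patient correlation 0.8 and a mean of 0.39 mM, about 21% of pump patients would still be over the limit after three attendances, so the rescheduling scenario is an idealisation.

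**Conclusion.** The point holds conditionally and is of low severity. If the limit is applied at Visit 6 and plasma follows only the described order, the week-12 fasting ketone value is selected on one of its own components, mainly in dapagliflozin-treated pump patients, and the week-12 contrast is biased towards no effect. Illustrative size at an assumed 50% pump share with unlimited rescheduling: about 6–33% of the week-12 rise, or about 1–8% if the effect is averaged over visits. The direction is firmer than the size, which the documents cannot fix.

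Weeks 1, 4 and 8 and all injection patients are unaffected. The limit at week 0 also selects pump patients, but it acts before treatment and so does not bias the comparison between arms.

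**What to change.** **Section 10.1, Visit 6:** draw and store fasting blood and spot urine from every patient on arrival at the first week-12 attendance, before any go/no-go decision on the acute test. Injection patients are already sampled without reference to that decision.

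**Section 17.1:** use that sample as the week-12 fasting value for the primary and other fasting endpoints, whether or not the acute test goes ahead. Keep the sample taken after the insulin stop as time 0 for the 0–6 hour AUC. Leave the safety limit unchanged. It would also help to say whether the limit applies at Visit 6, but the change works either way.

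**Cost:** one sentence in each section, with no new visit or assay. There are three downsides:
- Deferred patients have one extra draw.
- The week-12 fasting draw falls minutes before the insulin stop rather than just after it, as at week 0.
- Week 12 has no limit while week 0 does, which matters for the within-group paired tests. The ketone part should be small (under 1% over the limit at the pre-dapagliflozin level); the glucose part is unknown. The between-arm comparison is unaffected, because the week-0 limit acts before treatment.

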## **22.0 Potential Benefits to Subjects**

22.1 Describe the potential benefits that individual subjects may experience by taking part in the research. Include the probability, magnitude, and duration of the potential benefits. Indicate if there is no direct benefit.

NOTE: Compensation **cannot** be stated as a benefit.

Response: There are no potential benefits individual participants will experience.

## 23.0 Compensation for Research-Related Injury

- N/A: The research procedures for this study do not present risk of research related injury (e.g. survey studies, records review studies). This section does not apply.

23.1 *If the research procedures carry a risk of research related injury, describe the available compensation to subjects in the event that such injury should occur.*

Response: Routinely, Buffalo General Hospital, Erie County Medical Center, and/or the University at Buffalo, State University of New York, its agents, or its employees do not compensate for or provide free medical care for human subjects/participants in the event that any injury results from participation in a human research project. In the unlikely event that they become ill or injured as a direct result of participating in this study, they may receive medical care, that will be covered by study.

23.2 *Provide a copy of contract language, if any, relevant to compensation for research related injury.*

NOTE: If the contract is not yet approved at the time of this submission, submit the current version here. If the contract is later approved with **different language regarding research related injury**, you must modify your response here and submit an amendment to the IRB for review and approval.

Response: AstraZeneca shall reimburse the Institution for the direct, reasonable and necessary medical expenses incurred by the Institution for the treatment of any personal injury that is a direct result of adverse drug experiences to subjects resulting directly from any manufacturing defects in the Study Drug to which the Subjects would not have been exposed but for their participation in the Study if (i) the Institutional parties have complied with this Agreement, the Protocol and any written instructions of AstraZeneca concerning the Study Drug and (ii) all the requirements of informed consent have been complied with. AstraZeneca will not provide compensation for lost wages or for any other damages, expenses or losses, or for medical expenses that have been covered by a Subject's medical or other insurance.

